#### ***2.1 Design of tDCS-Only Study***

This is a sham-controlled, full cross-over study design. All subjects with PPA will participate in ten 20-minute tDCS stimulation sessions over the course of 2 weeks using 1.5 mA current. A battery of language tasks will be administered before stimulation sessions, after the 10 sessions, and again at 6 and 12 weeks after the stimulation sessions. The 12-week follow up session will serve as the "baseline" session for the following stimulation sessions. All subjects will also participate in ten 20-minute sham stimulation sessions over the course of 2 weeks. During sham tDCS, a 1.5 mA current will be delivered for approximately 30 seconds at the beginning of the sham session before being extinguished over the course of seconds. Participants will be randomly assigned to receive sham or tDCS stimulation first.

For example, a subject who is assigned to sham stimulation sessions first will first undergo baseline language testing. Then the subject will participate in ten 20-minute sham stimulation sessions over the course of 2 weeks. The subject will go through follow up language testing after the 10th sham stimulation sessions as well as 6 and 12 weeks following the sham stimulation sessions. The 12 week follow up session will serve as the "baseline" for the tDCS stimulation sessions, after which the subject will participate in ten 20-minute tDCS stimulation sessions over the course of 2 weeks, using 1.5 mA current.

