## ***3.1 Study Duration of tDCS-Only Study***

We expect this project to last for approximately 2 years. We expect to enroll approximately 10 subjects annually. Duration of subjects' participation in the study will be approximately 8-10 months.

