members of a specific category; semantic categories will include tools, animals, and vegetables. Subjects will also be asked to generate words starting with the letters F, A and S. - Repetition, Reading and Writing (single words) will be assessed using the materials developed by the NACC-FTD consortium; subjects are asked to read, write and repeat a series of words controlled for variables known to influence performance such as length, part of speech (noun, verb), imageability (desk vs. fate), age of acquisition, etc. - Elicited Speech Production: Speech samples will be elicited from subjects by presenting a picture book (e.g., Frog story) or scene to be described (Cookie Theft picture from the Boston Diagnostic Aphasia Examination) and asking subjects to describe what they see. Speech production will be scored off-line with respect to fluency (words/minute), grammatically well-formed sentences, mean length of utterance, nouns/100 words, verbs/100 words, phonemic errors, and phonetic errors. Half of subjects will undergo 10 sessions of sham stimulation first and will then undergo 10 sessions of real tDCS stimulation. Half of subjects will undergo 10 sessions of real tDCS stimulation first and will then undergo 10 sessions of sham stimulation. A complete language assessment will be performed before stimulation sessions, after the 10th stimulation session, and 6 and 12 weeks ( $\pm$  1 week) after the completion of stimulation sessions. Real tDCS stimulation will be administered using our standard apparatus (Magstim Eldith with 5x5 cm electrodes) using a current of 1.5 mA. (As a frame of reference, we routinely use 2 mA current in other studies.) The anode will be placed over the left fronto-temporal region of the brain and the cathode over the left occipito-parietal region. During sham stimulation, a 1.5 mA current will be delivered for approximately 10 seconds at the beginning of the sham condition before being extinguished over the course of seconds. As there is some evidence that engaging in the activity that one wishes to enhance while undergoing tDCS improves outcome, all subjects will be shown a children's picture book (e.g., the illustrated version of Cinderella) during the 20 minute period of stimulation and asked to narrate the story, regardless of whether they are in real tDCS stimulation or sham stimulation. Participants assigned to receive sham treatment first will cross over to real tDCS treatment after the 12-week follow up session. Each participant will then receive real tDCS stimulation for 10 sessions over the course of two weeks. The stimulation parameters and testing during treatment will be identical to the previous stimulation sessions, except this time participants will receive real tDCS stimulation instead of sham stimulation. Participants assigned to receive real tDCS stimulation first will cross over to sham stimulation after the 12-week follow up session. Each participant will then receive sham stimulation for 10 sessions over the course of two weeks. The stimulation parameters and language testing during treatment will be identical to the previous stimulation sessions, except this time participants will receive sham stimulation instead of real tDCS

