### **1.2 Procedures for HD-tDCS+CILT Sub-study**

After obtaining informed consent, a baseline language assessment will be performed twice, on separate days, for all subjects, regardless of whether they will be assigned to sham or real HD-tDCS stimulation first. The assessment will include some of the previously listed tests, LTROG, Pyramids & Palm Trees, Word Reading, Sentence Writing, and Sentence Repetition. The Western Aphasia Battery will also be administered. The *Western Aphasia Battery* (WAB: Shewan & Kertesz, 1980) samples a number of different language functions and generates a summary score between 0-100 (Aphasia Quotient, AQ), interpretable as general aphasia severity. They will also be given a 60-item screening/probe image set with 4 categories of picture-naming difficulty. There are, from easiest to most difficult: 1) High Frequency Objects, 2) Low Frequency Objects, 3) High Frequency Actions, and 4) Low Frequency Actions. Participants must perform at a rate of at least 50% picture-naming accuracy in the easiest category (High Frequency Objects) at *both* baseline assessments in order to be enrolled in the study. This is because we will start the therapy at the easiest category where we observed 50% accuracy in naming performance; if participants do not reach this level of accuracy in the easiest category of images, they may be too impaired to participate in the therapy without the therapy itself eliciting undue frustration, fatigue, etc. Subjects will also receive the Communicative Activity Log (CAL; Pulvermuller et al., 2001), which assesses the degree to which patients engage in spontaneous communicative behaviors in their day-to-day life. The items will

address speech output and language comprehension. We will also administer a pen-and-paper version of the CAL to participants' primary caregiver (spouse or family member as relevant) at each time-point. Subjects will undergo this combination of assessments on 9 different study visits, as outlined in the study schedule below. This total of nine assessment visits involves two additional assessment visits compared to the tDCS only (i.e., no therapy) study, due to the addition of two, separate, pre-tDCS baseline assessments.

Visits 1 and 2	Visit 3	Visits 4-11	Visit 12		Visit 13	
Baseline language testing and screening	Baseline language testing; Begin HD-tDCS+CI LT	HD-tDCS+CI LT	HD-tDCS+CI LT; Post-HD-tDCS language testing	(6 week break)	Post-HD-tDCS language testing	(6 week break)

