## **2. Statistical Analysis**

Data from each subject will be analyzed using a within-subject design in which change in performance from the baseline testing session to the post-therapy (0, 6, 12 weeks post tDCS) will be compared using t-tests, ANOVAs and other univariate statistics. As it is most relevant to real-world behavior, elicited speech production will serve as the primary endpoint. Depending on our ability to recruit a reasonable sample, group analyses will be also be performed. Finally, we note that high quality imaging will be available for the majority of subjects. Note that we are not proposing to obtain imaging under the auspices of the present study; this data will be available from [name] previously cited protocol. We will perform exploratory analyses in which we attempt to determine if specific imaging parameters (e.g., cortical thickness, degree of atrophy) predict response to tDCS.

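### T-tests and ANOVAs on complete rows would drop about 14–19% of subjects from the active-versus-sham contrast at an assumed 5% miss rate per visit, with selection on outcome; a mixed model would use their data

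*Combined protocol and SAP*

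**What the plan says.** Study Procedures, section 2 (Statistical Analysis) describes a within-subject comparison of "change in performance from the baseline testing session to the post-therapy (0, 6, 12 weeks post tDCS") by "t-tests, ANOVAs and other univariate statistics". Group analyses are added only if recruitment allows. The section on primary outcome variables is just as open and gives ANOVA and the t-test as examples. Neither section states the ANOVA factors, whether one analysis spans both periods, the analysis population, or how missed visits are handled.

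On the schedule, section 1.1 of the procedures (tDCS-Only) says "A complete language assessment will be performed before stimulation sessions, after the 10th stimulation session, and 6 and 12 weeks" after stimulation ends, in each of two periods. Section 1.2 (HD-tDCS+CILT) says "Subjects will undergo this combination of assessments on 9 different study visits" and adds "This total of nine assessment visits involves two additional assessment visits compared to the tDCS only (i.e., no therapy) study", which leaves seven for tDCS-Only. The periods share a visit: "The 12-week follow up session will serve as the 'baseline' session for the following stimulation sessions" (section 2.1, Design of tDCS-Only Study). In HD-tDCS+CILT a naming threshold must be met at both "baseline assessments in order to be enrolled in the study".

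On size, section 3.1 says "We expect to enroll approximately 10 subjects annually" for about two years. Section 3.2 says the same of HD-tDCS+CILT. The Accrual section says there is no basis for a sample size.

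All three procedures sections provide for discontinuation when language worsens. In HD-tDCS+CILT the trigger is a fall of 5 or more points on the Western Aphasia Battery. In the other two it is significantly worse performance at the one-week check.

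**The concern.** A paired t-test or a classical repeated-measures ANOVA needs a complete row for each subject. A subject who misses one required visit leaves the analysis, and the scores already collected from that subject go unused. The shared visit makes this worse: a missed 12-week visit in period 1 removes that outcome and also the reference for every period-2 change score. The schedule runs for at least 2 + 12 + 2 + 12 = 28 weeks in a progressive disease.

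Two things are at stake. One is precision, in a sample where each subject is about 1/20 = 5% of the total. The other is selection. A subject stopped in period 1 for worsening has no period-2 data and drops out of any complete-row crossover contrast, so the analysed group is chosen partly by outcome.

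**Working it through.** **Inputs.** The documents give no miss rate, dropout rate or power calculation, so there is no planned figure to reproduce.
- Assessments: HD-tDCS+CILT visits 1, 2, 3, 12, 13, 14, 23, 24 and 25 = 9. tDCS-Only has baseline, 0, 6 and 12 weeks (the last is also the second baseline), then 0, 6 and 12 weeks = 7.
- Expected subjects: about 10 a year × about 2 years = about 20 in each of these two studies.
- Miss rate m: assumed 5% per visit, with a range below.

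The svPPA sub-study is left out of the arithmetic. It has no accrual figure, and its design and procedures sections give different follow-up times.

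**Visits needed (k).** At 12 weeks the active-versus-sham contrast of change needs the first baseline, the shared 12-week visit and the final 12-week visit: k = 3. At 0 or 6 weeks it needs both baselines and one post-treatment visit in each period: k = 4. An ANOVA over the whole tDCS-Only schedule needs k = 7, or 6 if the first baseline is always present. In HD-tDCS+CILT the two screening baselines are a condition of enrolment, so at most 9 − 2 = 7 visits can be missed, or 6 if the visit 3 baseline is also always held.

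**Loss with independent misses.** Loss = 1 − (1 − m)^k; standard error factor against full data = 1/√(1 − loss). At m = 5%:

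| Analysis | k | Loss | Left of 20 | SE factor |
|---|---|---|---|---|
| One change score | 2 | 1 − 0.95² = 9.8% | 18.1 | 1.05 |
| Active vs sham, 12 weeks | 3 | 1 − 0.95³ = 14.3% | 17.2 | 1.08 |
| Active vs sham, 0 or 6 weeks | 4 | 1 − 0.95⁴ = 18.5% | 16.3 | 1.11 |
| All visits, one baseline certain | 6 | 1 − 0.95⁶ = 26.5% | 14.7 | 1.17 |
| All visits | 7 | 1 − 0.95⁷ = 30.2% | 14.0 | 1.20 |

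If the first baseline is taken as certain in the two contrasts as well, each needs one visit fewer, and the losses become 9.8% and 14.3%.

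**Range for m** (k = 3, 4, 7): 1% gives 3.0%, 3.9%, 6.8%; 2% gives 5.9%, 7.8%, 13.2%; 10% gives 27.1%, 34.4%, 52.2%.

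**Clustered misses.** Let a subject's own miss rate follow a beta distribution with mean 0.05 and intra-subject correlation r, so a = 0.05(1 − r)/r and b = 0.95(1 − r)/r. The chance of missing none of k visits is the product of (b + j)/(a + b + j) for j = 0 to k − 1. For r = 0.1, 0.3 and 0.5 the four-visit loss is 16.2%, 12.7% and 10.1%; the seven-visit loss is 24.1%, 16.9% and 12.3%.

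**Selection.** The documents give no discontinuation rate, so this part has no size. Its direction also cannot be fixed, because a stop for worsening can occur under active or sham stimulation.

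**The case against.** The plan commits neither to an ANOVA over all visits nor to a complete-case rule. It describes changes from baseline, lists t-tests, and leaves room for other methods. Group analyses are conditional. The 20 is an accrual expectation, not a target. The 5% is a reviewer's assumption, and independence sits badly with the idea that the more impaired subjects miss visits, since that implies clustering and a smaller loss. All of this stands, and it is why the main figures are those of the three- and four-visit contrasts.

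A reader might infer that the ANOVA needs all seven or nine visits and so loses 30–37%. The documents do not support this. No such ANOVA is specified. Nor can the 37% (1 − 0.95⁹) occur, because an enrolled HD-tDCS+CILT subject has already completed the two screening baselines. The battery listed for that sub-study also does not name elicited speech production, the primary endpoint, so its figure is a visit count and is not tied to that endpoint.

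A reader might also infer that a mixed model keeps everyone at full value. It keeps them in the fit. A subject with one period adds little to a within-subject contrast, and the standard error factors above compare complete cases with fully observed data, not with a mixed model on the same incomplete data.

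The objection does not remove the need for complete rows. Even the narrowest active-versus-sham contrast needs three visits, and the discontinuation rule ties missing rows to the outcome.

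**Conclusion.** The concern holds in a limited form. For the group analyses, the named methods discard subjects who lack any visit that the contrast needs. At an assumed 5% independent miss rate the active-versus-sham contrast loses 14.3% (12 weeks) or 18.5% (0 or 6 weeks, standard error about +11%) of about 20 subjects. If an ANOVA over all visits is meant, the loss is about 26–30% in tDCS-Only and HD-tDCS+CILT alike. With the same 5% mean and correlation of 0.1 to 0.5 within subjects, the seven-visit loss is about 12–24%. Discontinuation for worsening means that the complete cases are also selected on outcome, to an unknown extent. The visit counts come from the documents; the miss rate, its independence and the correlations are assumptions. The change should be made, but it does not decide whether the trial can be interpreted.

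**What to change.** For the group analyses, replace the t-tests and ANOVAs with a linear mixed model on all available assessments of all randomised subjects:
- Enter each assessment once. Code the shared visit as the period-1 12-week score and use it as the reference for period-2 change.
- Fixed effects: visit and sequence-by-visit, with the first baseline constrained equal between sequences. For HD-tDCS+CILT, state which pre-stimulation assessment is the period-1 baseline.
- Random subject and subject-by-period effects, with Kenward-Roger degrees of freedom.
- Estimand: the active-minus-sham difference in change from the period baseline at 0, 6 and 12 weeks, averaged over the two sequences.
- Report the complete-case result as a sensitivity analysis, and state the visits that each contrast needs.

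Treatment, visit and period as main effects alone would not do. The treatment term would then average over pre-stimulation baselines, the shared visit would have no clear place, and the planned change from baseline would not be estimated.

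The model is valid if missingness depends on observed scores that are in the model. The scores that trigger discontinuation should therefore be among the data used where they measure the endpoint; where they do not, the assumption is weaker and the report should say so.

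The cost is slightly more analysis work and reliance on a simple covariance structure. An unstructured one over seven visits has 7 × 8/2 = 28 parameters, too many for about 20 subjects.

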### **1.2 HD-tDCS+CILT Sub-study Objectives**

The objective of the HD-tDCS+CILT sub-study is to improve language function in patients with Primary Progressive Aphasia using a combination of HD-tDCS and a form of intensive speech therapy called Constraint-Induced Language Therapy. The HD-tDCS+CILT sub-study shares many of the design features of the tDCS-Only study in 1.1, therefore, we will include additional information about HD-tDCS+CILT in its own section where relevant to help delineate the differences between these two studies. Any sections that do not include a HD-tDCS+CILT sub-section apply identically to both studies.

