
tDCS+CILT session will be from a more difficult category (e.g., moving from high to low frequency objects, or from low frequency objects to high frequency actions, and so on). Sessions will be audio-recorded and performance will be scored across cuing levels. The CILT sessions will last up to 1.5 hours each, with HD-tDCS terminating after 20 minutes of stimulation.

Safety and tolerability of the treatment will be assessed in several manners. First, the inclusion/exclusion screening form will be administered both at the initial intake session, as well as at the first session of each 2-week stimulation block. Second, subjects will be queried about new symptoms or adverse effects prior to stimulation on all days when stimulation will be given; should subjects have any concerns, HD-tDCS will not be performed and language will be assessed with fluency tests, naming and a speech sample will be elicited. Third, language will be assessed immediately following the 10th HD-tDCS+CILT session with the WAB, the 60-item image set, and the patient/caregiver CAL. Should there be a clinically significant decrease in performance on the WAB (a reduction in score of **5 or more points**) compared to the participant's WAB score on day 1 of the treatment, the participant's visits will be discontinued; in this event, subjects will be followed on a weekly basis for 4 weeks or until performance returns to baseline (whichever comes first). We propose to use a "significant" change in performance as a cut-off because performance in this condition in the absence of any intervention is quite variable.

After the final visit of the HD-tDCS+CILT sub-study (i.e., the last 12-week follow-up), participants will have the option to participate in one additional round of 10 HD-tDCS+CILT sessions, to be scheduled no earlier than 3 months after study completion and no later than 6 months following study completion.

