### **1.3 Procedures for tDCS with svPPA Sub-Study**

After obtaining informed consent, a baseline language assessment will be performed twice, on separate days, for all subjects, regardless of whether they will be assigned to sham or real tDCS stimulation first. Depending on the subject, this assessment is expected to take 1-2 hours. Performance will be audio-recorded. The assessment will include the following measures:

- Global Cognition: we will administer the Montreal Cognitive Assessment, a commonly used measure of cognitive abilities.
- Semantic Memory: Pyramid and Palm trees: a well-standardized test in which subjects see 3 pictures or words on a page and are asked which two "go together"; for example on one

page, the pictures include a drawing of a glove, hand and foot.

- Category fluency: a series of tasks in which subjects are asked to generate as many words as possible in one minute that are members of a specific category; semantic categories will include tools, animals, and vegetables.
- Executive Processing: The Digit Symbol task from the Wechsler Adult Intelligence scale will be administered to test sustained attention and executive ability. Subjects will also be asked to generate words starting with the letters F, A and S.
- Naming: The Peabody Picture Vocabulary Test (PPVT-IV) and the Philadelphia Naming Test (PNT) will be administered, both commonly used tests to assess naming and general language ability.

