Half of subjects will undergo 10 sessions of sham stimulation first and will then undergo 10 sessions of real tDCS stimulation. Half of subjects will undergo 10 sessions of real tDCS stimulation first and will then undergo 10 sessions of sham stimulation. A complete language assessment will be performed before stimulation sessions, after the 10th stimulation session, and 12 weeks and 6 months ( $\pm$  1 week) after the completion of stimulation sessions. Real tDCS stimulation will be administered using the Soterix 1x1 using a current of 2 mA. The cathodal current will be split across two electrodes (5cm^2) positioned over the left and right temporal regions respectively. The anodal electrode (5x7cm) will be placed over the forehead. During sham stimulation, a 2 mA current will be delivered for approximately 10 seconds at the beginning of the sham condition before being extinguished over the course of seconds. After the first 10 minutes of stimulation, in both real and sham conditions, participants will begin the behavioral treatment, which will continue for 45 minutes; therefore there will be 20 minutes of concurrent tDCS and behavioral therapy.

Prior to initiating treatment, we will craft an individualized training lexicon for each patient. This training vocabulary contains familiar people, household items, foods, activities, cloths, and hygiene implements. Target words are represented by photographs of the patient's own items. We will employ several item-level controls to examine treatment generalization. The first will test the impact of personal familiarity by asking patients to name and generate features for canonical rather than personal photographs. The second condition will evaluate within-category generalization by asking patients to name and generate features for their own untrained items. The final item-level comparison will examine generalization of naming accuracy to untrained

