Safety and tolerability of the treatment will be assessed in several manners. First, the inclusion/exclusion screening form will be administered both at the initial intake session, as well as at the first session of each 2-week stimulation block. Second, subjects will be queried about new symptoms or adverse effects prior to stimulation on all days when stimulation will be given; should subjects have any concerns, tDCS will not be performed and language will be assessed with fluency tests, naming and a speech sample will be elicited. Third, in the absence of symptoms, language will be assessed at the end of one week of treatment with picture naming, fluency measures and a speech sample will be elicited. Should performance be significantly worse than prior to initiation of treatment, the study will be discontinued; in this event, subjects will be followed

on a weekly basis for 4 weeks or until performance returns to baseline (whichever comes first). We propose to use a "significant" change in performance as a cut-off because performance in this condition in the absence of any intervention is quite variable.

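### The HD-tDCS+CILT battery as listed omits elicited speech, the stated primary endpoint; for svPPA the primary endpoint is left unsettled

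*Combined protocol and SAP*

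**What the plan says.** All places are in the combined protocol and SAP.

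- **Endpoint.** Section 2, Statistical Analysis, is the only analysis section. It states that "elicited speech production will serve as the primary endpoint", on the ground that this is closest to everyday behaviour. The contrast is change from baseline to 0, 6 and 12 weeks after stimulation. No sub-study is given its own rule.
- **Scope.** Objectives 1.2 states: "Any sections that do not include a HD-tDCS+CILT sub-section apply identically to both studies". Statistical Analysis has no such sub-section. Objectives 1.2 does not mention svPPA.
- **The task itself.** Procedures 1.1 (tDCS-Only) defines Elicited Speech Production as a picture-book or scene description, scored off-line in seven ways.
- **HD-tDCS+CILT battery.** Procedures 1.2 states: "The assessment will include some of the previously listed tests, LTROG, Pyramids & Palm Trees, Word Reading, Sentence Writing, and Sentence Repetition". It adds the WAB, a 60-item picture-naming set and the CAL questionnaire, and continues: "Subjects will undergo this combination of assessments on 9 different study visits". The assessment after the tenth session is listed as the WAB, the image set and the CAL. A speech sample appears only for days on which a subject raises concerns: "HD-tDCS will not be performed and language will be assessed with fluency tests, naming and a speech sample will be elicited".
- **svPPA battery.** Procedures 1.3 lists the MoCA, Pyramid and Palm Trees, category fluency, Digit Symbol and F/A/S fluency, and ends with "Naming: The Peabody Picture Vocabulary Test (PPVT-IV) and the Philadelphia Naming Test (PNT) will be administered". Its safety text adds, for subjects without symptoms, "language will be assessed at the end of one week of treatment with picture naming, fluency measures and a speech sample will be elicited". It also provides for a speech sample on days when a subject has concerns.
- **General outcome statement.** Objectives section 2, Primary Outcome Variable(s), mentions naming and picture description among a range of language measures. It singles out no score.

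**The concern.** A change-from-baseline endpoint needs the same measurement before and after treatment. In HD-tDCS+CILT the designated measurement is missing from the list that staff would work from. Naming, reading, writing, repetition and questionnaire scores do not supply the connected-speech quantities in Procedures 1.1, such as words per minute or mean length of utterance.

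Two things are at stake. First, the pre-treatment sample is lost for good once the first block starts. Second, if the designated endpoint turns out not to exist, the main result will have to be picked from the other scores after the data are in. The second risk also arises in svPPA if the analysis section was never meant to cover it.

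**Working it through.** The plan gives no figure to reproduce on this point, so the check sets each list of instruments against the endpoint.

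**Instruments named, and whether elicited speech is among them**

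| Study | Source | Named instruments | Elicited speech |
|---|---|---|---|
| tDCS-Only | Procedures 1.1 | full list, including speech | yes |
| HD-tDCS+CILT | Procedures 1.2 | 5 carried over + WAB + image set + CAL = 8 | 0 of 8 |
| svPPA | Procedures 1.3 | MoCA, Pyramid and Palm Trees, category fluency, Digit Symbol, F/A/S, PPVT-IV, PNT = 7 | 0 of 7 |

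Procedures 1.3 later adds baseline naming accuracy on the personal items and eye-tracking. Neither is a speech sample.

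**Time points in HD-tDCS+CILT.** From the visit table in Procedures 1.2, language testing falls at visits 1, 2, 3, 12, 13, 14, 23, 24 and 25, which is 9 visits. The post-therapy points in the analysis section are 0, 6 and 12 weeks after each of 2 blocks: 3 × 2 = 6 (visits 12, 13, 14 and 23, 24, 25). As listed, none of the 6 has an elicited-speech score, and neither does any of the three pre-treatment visits.

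**Time points in svPPA.** No count of affected points is claimed, because the schedule differs between sections. Design 2.2 for svPPA has testing after block 1, at 12 weeks, after block 2, and then at 6 and 12 weeks. Procedures 1.3 has "A complete language assessment will be performed before stimulation sessions, after the 10th stimulation session, and 12 weeks and 6 months". Neither schedule fully matches the 0, 6 and 12 weeks of the analysis section, which is a further reason to doubt that the section was written with svPPA in mind. Two cases remain:

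1. The analysis section governs svPPA. Its endpoint is then not in the listed battery.
2. It does not govern. svPPA then has no single designated primary endpoint, because the general outcome statement names a range of measures and selects none.

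**Week-1 safety check in svPPA.** Three kinds of measure are taken: naming, fluency and a speech sample. Naming and fluency have listed pre-treatment values, so 2 of 3 have a comparator and 1 of 3 does not.

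**The case against.** The strongest reply is that the lists were not meant to be exhaustive. Both sub-study batteries are introduced as what the assessment will include, and Procedures 1.2 and 1.3 each promise a complete assessment without defining it. The general outcome statement mentions picture description, which is one of the elicited-speech tasks and has no sub-study exception. The svPPA safety text elicits speech at week 1 and compares performance with the pre-treatment state, which suggests that an earlier sample was intended. All of this stands as evidence of intent. But none of it adds the task to either battery or names a score. Procedures 1.1 uses the same introductory wording and then spells out the speech task in detail, while Procedures 1.2 says that only some of those tests are kept and names which.

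On scope, Statistical Analysis is item 2 within Study Procedures, and Study Procedures as a whole does have an HD-tDCS+CILT part. The scope sentence could therefore be read as not reaching it. That reading is possible but less natural, and it would leave the sub-study with no analysis section at all.

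The WAB may contain connected speech. The documents describe it only as sampling several functions and giving a 0–100 summary, so this remains open. Treatment sessions are audio-recorded, but they capture cued card requests of adaptive difficulty and not a standard sample at outcome visits.

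Three stronger readings are tempting and are not supported:

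- **That the endpoint certainly cannot be computed.** It cannot be computed from the lists as written, but the lists may be incomplete.
- **That svPPA contradicts the analysis section in the same way as HD-tDCS+CILT.** No sentence carries that section to svPPA.
- **That the svPPA safety rule fails for lack of a speech baseline.** The rule refers to performance generally, and naming and fluency still have comparators.

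**Conclusion.** The point holds for HD-tDCS+CILT: the stated primary endpoint is in none of the 8 named instruments, so if the lists are followed the primary change score is missing at all 6 post-therapy points. This rests on two assumptions: that the scope sentence in Objectives 1.2 reaches Statistical Analysis, and that staff collect what is listed.

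For svPPA the finding is a required clarification: either the endpoint is absent from the battery or no single primary endpoint has been set. The safety consequence is small.

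The plan gives no basis for a sample size (section 2, Accrual), and group analyses depend on recruitment. Fixing the endpoint will not by itself make the sub-studies conclusive, but within-subject change also needs the measurement. The correction should be made. Confidence is medium, because of the possible incompleteness of the lists.

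**What to change.** Settle this in writing before the next subject's baseline.

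**HD-tDCS+CILT, one of:**

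- Add the Procedures 1.1 picture description, scored the same way, at all 9 assessment visits and at the booster assessments for those who opt in. Name one of its seven scores as primary.
- Name a score already collected, such as the WAB Aphasia Quotient. The stopping rule in Procedures 1.2 withdraws subjects whose WAB score falls by 5 or more points, so the plan should also say that the score triggering withdrawal stays in the analysis.

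**svPPA:** State whether Statistical Analysis applies, then do one of:

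- Add the same sample at every baseline and later assessment, and name one score as primary.
- Name a naming score already collected. The PNT is available, but Procedures 1.3 uses it to test generalization to untrained items. It would not measure gains on the trained items.

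If no baseline sample is added in svPPA, remove the speech sample from the week-1 comparison.

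**Cost.** The documents give no duration for a sample, so 5 to 10 minutes is assumed.

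- HD-tDCS+CILT: 9 × 5 = 45 to 9 × 10 = 90 minutes per subject. A booster round with at least one baseline plus 0, 6 and 12 weeks adds 4 × 5 = 20 to 4 × 10 = 40 minutes.
- svPPA, taking the two baselines from Procedures 1.3 and the later visits from Design 2.2: 2 + 5 = 7 sessions, or 35 to 70 minutes. With the Procedures 1.3 schedule read per block: 2 + 3 × 2 = 8 sessions, or 40 to 80 minutes.

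Off-line scoring time comes on top, and the sessions become longer. Naming an existing score adds no testing, but it gives up the measure that the plan regards as closest to everyday language.
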